**ID Number: NCT05277389**

**Document Date: 06/07/2024**

## **Study Protocol & Statistical Analysis Plan**

We will conduct a stratified, parallel-group, double-blind, randomized controlled trial of remotely delivered START treatment to individuals with severe-to-moderate stroke (with recruitment focused on individuals with low SES). Subjects and assessors will be blinded to the condition making the experiment double blind. Specifically, subjects will be told that we are exploring a new therapy that uses different sounds to improve therapy. Parallel group design will ensure that subjects in the Control group are unaware that their “sounds” are softer than the START group. Trainers may become aware that a loud sound is present thus unique Assessor will evaluate clinical performance before and after training. Assessor will be a certified and practicing occupational therapist.

Fifty-eight subjects will undergo baseline testing in the laboratory to establish their upper extremity impairment, spasticity, and function as well as their self-reported health-related quality of life. Next, subjects will participate in high-repetition training, 2 hr/day for 3 consecutive days focusing on functional object manipulation (details below). Subjects will either receive training with START or without (Control). Subjects will be re-tested immediately following training as well as one-month post to assess retention. Activity trackers will be deployed before (baseline), during, and after training. Aim 1 will evaluate the ability of START to enhance therapy outcomes by assessing the % change clinical assessment of function, spasticity, impairment, and self-reported quality of life, functional independence, and arm usage. Aim 2 will focus on the capacity of these changes to 1) be retained and 2) impact subject’s self-reported quality of life. *NOTE:* While we are planning in-person baseline, end, and retention testing, in response to covid, we have established remote clinical screening (see Potential Challenges and Solutions).

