We hypothesize that training with START will increase paretic arm function (ARAT), self-reported arm function (MAL), and functional independence (mRS) compared to training without START. To assess this, we will evaluate effects of the treatment (START vs control) on a group of random subjects from a parallel group of stroke patients. The hypothesis expects a positive impact over multiple days of evaluation with respect to the baseline. We do not expect the data to conform to Gaussian norms. Therefore, we will utilize a generalized linear mixed model to identify differences between groups in this longitudinal data set. The *treatment* (START vs. control) and the *day of testing* (pre, post) will be setup as the fixed factors. *Subjects* will be treated as a random factor, nested within treatment. Tukey post-hoc tests will be employed with a p-value <0.05 will be used to indicate significance. Analysis will be conducted using R's lme4 package.

**Analysis for Aim 2: To establish that START generates retainable changes that impact quality of life, we will re-assess upper-extremity function and self-reported quality of life (SIS, MRS).**

We hypothesize that A) START gains will be retained more than Control and B) retention will be associated with higher quality of life measures (e.g., SIS) one-month post-START training. For A, the same analysis as proposed above will be conducted except the *day of testing* will compare post-training to one-month post as the fixed factors. To complete the analysis for B, we will utilize a regression analysis between the change in the functional score and the change in the quality of life for each subject. The choice between a linear and a logistic regression will be determined by the data themselves. Analysis will be conducted in R, using the base R functionality.

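### The analysis for Aim 1 and Aim 2A names no deciding contrast: treatment and day are the only fixed factors, with no treatment-by-day term, no baseline-score adjustment and no definition of retention

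*Combined protocol and SAP*

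**What the plan says.** The section on the analysis for Aim 1 hypothesises that START improves ARAT, MAL and mRS more than training without START, and adds: "The hypothesis expects a positive impact over multiple days of evaluation with respect to the baseline". Because non-Gaussian data are expected, a generalized linear mixed model will be used "to identify differences between groups in this longitudinal data set". Treatment and day are the fixed factors; the day factor is introduced with the words "pre, post) will be setup as the fixed factors". Subject is a random effect nested in treatment. The decision rule is: "Tukey post-hoc tests will be employed with a p-value <0.05 will be used to indicate significance". No distribution or link is named.

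For Aim 2A the hypothesis is that "START gains will be retained more than Control". The analysis is the one used for Aim 1, except that the day factor "will compare post-training to one-month post as the fixed factors".

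The overview at the start of the document describes Aim 1 as "assessing the % change clinical assessment of function, spasticity, impairment, and self-reported quality of life, functional independence, and arm usage", and says: "Aim 2 will focus on the capacity of these changes to 1) be retained".

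**The concern.** The Aim 1 hypothesis is about a difference between arms in change from baseline, or equivalently in the post-training score given baseline. Nothing in the analysis section ties a model term or a pair of cells to that hypothesis. Several analyses fit the text and they do not answer the same question:

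1. **Additive model** (the two listed factors and nothing more), judged by the treatment term.
2. **Four treatment-by-day cells** judged by Tukey pairs, including START versus Control at post-training, or the two within-arm pre-to-post pairs read side by side.
3. **Factorial model** judged by treatment-by-day, with Tukey as follow-up.

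At stake for Aim 1 are the quantity estimated, the power, and the freedom to pick a reading once the data are in. Aim 2A inherits the gap and adds another: retaining more could mean a smaller absolute loss after training, more gain over baseline still present at one month, or a larger share of the gain kept. Finally, percent change per subject is one value per person, so it cannot be the response in a model with a pre level, and the analysis section names no link or transformation that would carry it.

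**Working it through.** **Inputs.** From the documents: 58 subjects (overview) and about 15% attrition (study population and screening). No effect size, SD, correlation, allocation ratio or power is given, so there is no stated power figure to reproduce. Assumed: 1:1 allocation (29 per arm), Gaussian outcome with unit SD at each visit, two-sided 0.05, true post-training effect d of 0.5 to 1.0 SD, correlation r between visits of 0.3 to 0.8.

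**What each Aim 1 reading estimates.** Randomisation makes the expected pre difference zero and the post difference d.
- Additive treatment term: (0 + d)/2 = d/2, exact with an identity link and complete data.
- Tukey over four cells: six pairs, none of which is a difference of differences. START versus Control at post has expectation d but ignores baseline.
- Treatment-by-day: d.
- Baseline-adjusted post score (not in the plan): d.

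**Power.** With v = 1/29 + 1/29 = 0.0690, the noncentrality parameters at d = 0.5, r = 0.5 are:
- additive: (d/2)/√(v(1+r)/2) = 0.25/0.227 = 1.10
- Tukey post pair: d/√v = 0.5/0.263 = 1.90, against a critical value of 2.65 (four-group studentized range divided by √2, 56 df) instead of 2.00
- treatment-by-day: d/√(2v(1−r)) = 0.5/0.263 = 1.90
- baseline-adjusted: d/√(v(1−r²)) = 0.5/0.227 = 2.20 (55 df)

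Noncentral-t power at d = 0.5:

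| r | Additive | Tukey post pair | Treatment-by-day | Baseline-adjusted |
|---|---|---|---|---|
| 0.3 | 21% | 24% | 35% | 50% |
| 0.5 | 19% | 24% | 47% | 58% |
| 0.8 | 17% | 24% | 84% | 88% |

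For equal power, treatment-by-day needs 2(1−r)/(1−r²) = 2/(1+r) times the subjects of the baseline-adjusted test: 1.54 at r = 0.3, 1.33 at 0.5, 1.11 at 0.8.

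**Type I error.** In 40,000 simulated null trials at each of r = 0.3, 0.5 and 0.8, the additive and treatment-by-day tests each rejected about 5% of the time, and the Tukey post pair about 1%. Reporting whichever of the three was significant gave about 10%.

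**Within-arm Tukey tests.** If both arms have the same true gain and each is significant with probability p, START is significant and Control is not with probability p(1−p). At a gain of 0.3 SD and r = 0.8, p is about 0.48, so this happens in about 25% of trials with no treatment effect.

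**Aim 2A, meaning of retention** (illustrative gains). START gains 10, Control gains 4, both then lose 2: treatment-by-day from post to one month is 0, gain still present is 8 v 2, share kept is 80% v 50%. START goes from a gain of 6 to 3 and Control from 2 to 1: treatment-by-day is −2, gain still present is 3 v 1, share kept is 50% in both. The meanings can disagree, and the share needs the baseline score, which is not in the Aim 2A model.

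**Aim 2A, additive term.** If START is ahead by d at post and level at one month, the treatment term estimates (d + 0)/2, with the same noncentrality as the Aim 1 additive term. It favours START significantly in 17% of trials (d = 0.5, r = 0.8) to 64% (d = 1.0, r = 0.3).

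**Aim 2A, absolute loss.** If the arms gain 1.0 and 0.4 SD and each keeps half, the losses are 0.5 and 0.2. The 0.3 difference has noncentrality 0.3/√(2v(1−r)) = 0.97 at r = 0.3 and 1.81 at r = 0.8, so treatment-by-day is significant against START in 16% to 43% of trials.

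**Percent change** (illustrative). START 10 to 15 and Control 20 to 28: raw changes are 5 and 8, a difference of −3; percent changes are 50% and 40%, a difference of +10 points. The scale decides the sign.

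**The case against.** The best defence is that the interaction was meant. The hypothesis refers to baseline, subjects nested within treatment is split-plot language in which the interaction is the usual test, and Tukey adds nothing to main effects with two levels each. On that reading Aim 1 is a valid randomised comparison, and START versus Control at post-training would be valid too. This stands: the additive model is the least likely intention, though it is what the listed factors literally give. The fault is therefore an unnamed contrast. A reader might infer that the plan commits to a wrong or invalid model, or that its tests exceed 5%. The text does not support either.

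A reader might also infer that percent change is incompatible with every reading. It is not: with a log link, treatment-by-day tests relative change in model means (1.50/1.40 = 1.07 in the example above). The supportable statement is that no link, transformation or percent-change response is named.

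Nor does hearing exhaust the plan's extra factors: the design is stratified and sex differences are to be examined. Neither is a baseline-score adjustment.

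It can be said that baseline adjustment is a preference over a valid interaction test. At high correlation the gain is indeed small (84% v 88% at r = 0.8); at r = 0.3 it is 35% v 50%. The baseline score is already collected. Finally, the power figures rest on assumed Gaussian inputs: they rank the readings and do not describe this trial's power, least of all for ordinal mRS.

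**Conclusion.** The point holds as an unspecified deciding contrast for Aim 1 and Aim 2A, and it should be fixed before analysis. For Aim 1, the readings the text allows range from 19% to 47% power at d = 0.5 and r = 0.5 with 29 per arm, and from 17% to 84% at r = 0.8; the literal reading also halves the estimand. Type I error is at risk only if the reading is chosen after seeing the data. For Aim 2A, the additive term matches no meaning of retention and can favour START after its advantage has gone. It might be inferred that absolute loss is the right default for retention; the documents do not define it so, and that choice can count against the arm that gained more even when both keep the same share. The percent change in the overview is unreconciled with the analysis section. All sizes depend on the assumed effect, correlation and 1:1 allocation.

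**What to change.** In the Aim 1 analysis, make the deciding test for each outcome the START-minus-Control difference in post-training score adjusted for the subject's own baseline score, with family and link fixed in advance. On an identity link, a treatment-by-day contrast in a mixed model with a common baseline mean for the two arms serves the same aim and keeps subjects who have no post-training score.

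For Aim 2A, the sponsor should choose one meaning of retention in advance (absolute change from post-training to one month, gain from baseline still present at one month, or share of gain kept) and name the matching contrast, including the baseline score where the meaning needs it. If absolute change is chosen, note that it can penalise the arm with the larger gain.

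Keep percent change as description, or state the model that tests it. State that side-by-side within-arm Tukey tests are not evidence of a treatment effect.

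Cost: a small change of model and no new data. The baseline-adjusted test has one record per subject, so it replaces the two-visit mixed model for Aim 1, and subjects without a post-training score drop out unless the common-baseline mixed model is used. Within-arm significance can no longer be offered as support.

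### The plan counts quality of life among the outcomes that evaluate START, but writes in no START-versus-Control comparison of SIS; the only named SIS analysis is a test of association

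*Combined protocol and SAP*

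**What the plan says.** The overview states: "Aim 1 will evaluate the ability of START to enhance therapy outcomes by assessing the % change clinical assessment of function". Its list goes on to spasticity, impairment, self-reported quality of life, functional independence and arm usage.

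Under Baseline Testing, SIS is described as a measure of health-related quality of life and three of its subdomains are to be used (hand function, ADL/IADL, mobility). mRS and MAL stand in the same list of measures. End- and Retention- Testing schedules SIS on the last training day and at one month.

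Analysis for Aim 1 puts the between-arm hypothesis on "paretic arm function (ARAT), self-reported arm function (MAL), and functional independence (mRS) compared to training without START". The model is a generalized linear mixed model with treatment and day (pre, post) as fixed factors. SIS is not named.

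The Aim 2 heading sets the goal "To establish that START generates retainable changes that impact quality of life" and names SIS and mRS as the quality-of-life measures. Two analyses follow:

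- **A** (retention, START against Control) reuses the Aim 1 model. The day factor "will compare post-training to one-month post as the fixed factors". No outcomes are listed.
- **B** states that "retention will be associated with higher quality of life measures (e.g., SIS) one-month post-START training". It is tested thus: "we will utilize a regression analysis between the change in the functional score and the change in the quality of life for each subject". No treatment term is named, and the interval over which change is taken is not given. On model form: "The choice between a linear and a logistic regression will be determined by the data themselves".

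**The concern.** The Aim 2 heading makes a claim about START and quality of life. A randomised trial supports such a claim by comparing the arms. For SIS, the measure that hypothesis B itself gives as its example, no such comparison is written in. An analyst following the text would report a slope between two change scores. Both changes can move together in every participant whether or not START did anything, so a significant slope could be reported under that heading with no evidence that START altered SIS.

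Aim 2A does not clearly close the gap. It refers back to the Aim 1 analysis, whose named outcomes are ARAT, MAL and mRS. Its contrast runs from end of training to one month, so a benefit reached by the end of training and then fully held is a difference of zero.

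**Working it through.** The plan gives no effect size, SD or power statement, so there is no figure of its own to reproduce. The check has a textual part and an illustrative part.

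**1. Outcomes set against analyses**

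| Measure | Named START-versus-Control analysis | Other named analysis |
|---|---|---|
| ARAT, MAL | Aim 1, pre/post | 2A if the same outcomes carry over; a functional score enters 2B |
| mRS | Aim 1, pre/post | 2A if carried over; listed as quality of life in the Aim 2 heading |
| SIS | none | 2B regression only |

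**2. Inputs for the illustration**

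- From the plan: 58 participants; about 15% attrition (given with the yearly recruitment estimate); p < 0.05.
- Assumed: equal allocation, two-sided tests, normal scores, the effects and correlations below.
- Analysed: 58 × 0.85 = 49.3, taken as 49 (25/24). The no-loss case is 58 (29/29).

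**3. Association and treatment effect are different questions.** With 29 per arm, a correlation of 0.5 between the changes and no START effect on either score, the 2B regression is significant in about 98% of simulated trials. The START-versus-Control test of SIS change rejects in about 5%.

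**4. A gain that is fully kept.** Let START raise SIS by 0.7 SD at end of training and at one month, with visit correlation 0.5. The expected arm difference in change from post to one month is 0.7 − 0.7 = 0. Simulated rejection rates:

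| Comparison of SIS | 49 analysed | 58 analysed |
|---|---|---|
| One month, adjusted for baseline | 78% | 85% |
| One month, unadjusted | 67% | 75% |
| Post-to-one-month change (2A contrast) | 5% | 5% |
| Treatment term of 2A (mean of both visits) | 79% | 86% |

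The 2A treatment term could show the gain, but the plan does not say that this term carries any claim, and hypothesis A is about retention.

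**5. Pooling the arms in 2B.** With no within-arm link, START shifts of d1 and d2 SD and near-equal arms, the pooled correlation is 0.25·d1·d2 / √[(1 + 0.25·d1²)(1 + 0.25·d2²)]. For equal shifts this is 0.25d² / (1 + 0.25d²):

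- 0.5 SD: 0.0625 / 1.0625 = 0.06; slope significant in 7% of trials
- 0.8 SD: 0.16 / 1.16 = 0.14; 16%
- 1.0 SD: 0.25 / 1.25 = 0.20; 29%

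These are for 49 analysed, with changes measured from baseline. At 0.3 SD the rate is 5%. With 0.8 SD on function and 0.3 SD on SIS it is 7%. With an arm term it is 5% throughout.

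**6. What the added comparison could detect.** The 95% half-width is t(0.975) × √(1/n1 + 1/n2), multiplied by √(1 − 0.5²) = 0.866 when adjusted, with one fewer degree of freedom.

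- 58: 2.003 × 0.2626 = 0.53 SD unadjusted; 0.46 SD adjusted
- 49: 2.012 × 0.2858 = 0.57 SD unadjusted; 0.50 SD adjusted

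The difference detectable with 80% power (noncentral t) is 0.75 SD (58) or 0.82 SD (49) unadjusted, and 0.65 or 0.71 SD adjusted.

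**The case against.** **Quality of life is already compared by arm.** The Aim 2 heading labels mRS a quality-of-life measure, and Aim 1 compares mRS between arms. This stands. A reader might infer that the plan has no randomised quality-of-life comparison at all; the documents do not support that. The gap is SIS.

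**SIS is plainly meant to be in the Aim 1 model.** The overview points that way, and adding SIS to the Aim 1 list would be the smallest repair. Under the assumptions above, the arm difference in pre-to-post SIS change would be detected in about 67% of trials with 49 analysed. The intention is plausible, but it is not written, and a pre/post comparison alone does not speak to quality of life at one month.

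**The regression is sound.** For the association that hypothesis B states, it is. A reader might infer that it is invalid, or that it must carry a treatment term. Neither follows. Hypothesis B refers to one month after START training, which may mean START participants only; then nothing is pooled and there is no arm term to add. If both arms enter, the inflation is material only for large effects on both scores. The arm term also has a price: with shifts of 0.5 SD and a within-arm correlation of 0.3, the chance of a significant slope falls from 68% to 55%. If START works on quality of life through function, the part removed is relevant signal.

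**2B could be aligned with 2A.** A reader might infer that 2B should take change from post-training to one month, as 2A does. The plan does not say so. On that interval a fully kept gain counts as no change, so the weakness of the 2A contrast would pass into 2B. The pooling inflation also vanishes there (about 5%, against about 12% to 29% from baseline for shifts of 0.7 to 1.0 SD).

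**The numbers come from outside the plan.** They do, and the plan expects non-Gaussian data. The textual gap does not depend on them.

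**Conclusion.** The concern holds for SIS. Followed as written, the plan evaluates START on quality of life, yet names no START-versus-Control comparison of SIS and leaves the association regression as the only named SIS analysis. That regression cannot attribute a SIS change to START, and the 2A contrast, even if SIS were entered, could not see a gain that is held. The sizes rest on assumed effects, an assumed visit correlation of 0.5, equal allocation and normal models standing in for the planned mixed model. The comparisons named in Aim 1 are unaffected. This is a correction worth making before analysis, not a flaw in the trial's design.

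**What to change.** 1. Add SIS to the between-arm outcomes in the analysis section, with one of the three subdomains named in advance as the lead. Compare START with Control at one month, and at end of training, adjusting for baseline SIS. Base any claim that START affects SIS on this comparison.
2. Keep the 2B regression as supportive evidence of association only. State whether it uses START participants or both arms. If both, report the slope with and without treatment arm.
3. Minor: state the interval over which the 2B changes are taken, and set linear or logistic form in advance by outcome type.

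The cost is SAP wording and one extra model; no new data or visits are needed. Precision is limited. With a baseline to one-month correlation of 0.5 (assumed), 80% power is reached only for about 0.65 SD (58 analysed) to 0.71 SD (49 analysed), so a non-significant SIS result should be reported with its confidence interval and not read as absence of effect.
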